9 ASSESSMENT OF SAFETY

9.1 Specification of Safety Parameters

The primary safety concern of this study is gastrointestinal tolerability of the azithromycin regimen, which is the most common AE associated with azithromycin and was the most common reported by males in the prior chlamydia treatment trial conducted in the same study population.¹⁶ Because safety of azithromycin was one of the study objectives of the previous chlamydia treatment trial and because no subjects receiving azithromycin withdrew due to an AE or experienced an SAE,¹⁶ we will not evaluate all AEs as an objective of the current study. However, because gastrointestinal tolerability of azithromycin could influence our efficacy outcome, we will collect data on reported gastrointestinal symptoms. We will also collect data on any SAE.

9.2 Methods and Timing for Assessing, Recording, and Analyzing Safety Parameters

9.2.1 Adverse Events

Gastrointestinal AEs that occur after study drug administration (Visit 1) and through the Day 28 follow-up visit (Visit 2) will be recorded on an AE case report form (CRF). AEs which cause a participant to discontinue from the study after study drug administration (Visit 1) and through the Day 28 follow-up visit (Visit 2) will be recorded on an AE CRF.

At the follow-up visit (Visit 2), subjects will be queried regarding the occurrence of any gastrointestinal side effects since enrollment visit, and any such AEs will be recorded in the subject's research chart and periodically monitored by the SI.

Adverse Event: An AE is defined as any untoward medical occurrence in a study subject administered a pharmaceutical product regardless of its causal relationship to the study treatment. An AE can therefore be any unfavorable and unintended sign, symptom, or disease temporally associated with the use of the study antibiotic regimens. The occurrence of an AE may come to the attention of study personnel during study visits and interviews of a study recipient presenting for medical care, or upon review by a study monitor.

AEs related to gastrointestinal reactions, including those not meeting the criteria for SAEs, should be captured on the Adverse Event CRF. Information to be collected includes event description, time of onset, clinician's assessment of severity, relationship to study product (assessed only by those with the training and authority to make a diagnosis, which would include MD, PA, Nurse Practitioner, DO, or DDS), and time of resolution/stabilization of the event. AEs must be documented appropriately regardless of relationship. All AEs will be followed to adequate resolution.

Pre-existing gastrointestinal conditions should be noted at baseline and not reported as an AE. However, if it deteriorates on or before the Day 28 follow-up visit (Visit 2), it should be recorded as an AE.

All AEs, as specified in Section 9.2.1, must be graded for severity and relationship to study product.

FDA defines an AE as any untoward medical occurrence associated with the use of a drug in humans, whether or not considered drug related.

Severity of Event: The following guidelines will be used to quantify intensity:

Gastrointestinal side effects which include nausea, vomiting, abdominal pain, and diarrhea will be assessed on a scale of 1 to 3 according to the toxicology table in Appendix B of this protocol.

Other AEs will be graded using the following general criteria:

- Mild: events require minimal or no treatment and do not interfere with the subject's daily activities.
- Moderate: events result in a low level of inconvenience or concern with the therapeutic measures. Moderate events may cause some interference with functioning.
- Severe: events interrupt a subject's usual daily activity and may require systemic drug therapy or other treatment. Severe events are usually incapacitating.

Changes in the severity of an AE will be documented to allow an assessment of the duration of the event at each level of intensity to be performed. Adverse events characterized as intermittent require documentation of onset and duration of each episode.

Relationship to Study Products: The SI's or provider's assessment of an AE's relationship to test article (study drug) is part of the documentation process, but it is not a factor in determining what is or is not reported in the study. If there is any doubt as to whether a clinical observation is an AE, the event should be reported. All AEs must have their relationship to study product assessed using the terms: related or not related. In a clinical trial, the study product must always be suspect. To help assess, the following guidelines are used.

- Related – There is a reasonable possibility that the study product caused the AE. Reasonable possibility means that there is evidence to suggest a causal relationship between the study product and the AE.
- Not Related – There is not a reasonable possibility that the administration of the study product caused the event.

9.2.2 Serious Adverse Events

An adverse event or suspected adverse reaction is considered “serious” if, in the view of either the investigator or sponsor, it results in any of the following outcomes:

- Death during the period of protocol defined surveillance
- Life Threatening adverse event (defined as a subject at immediate risk of death at the time of the event)
- An event requiring inpatient hospitalization or prolongation of existing hospitalization during the period of protocol defined surveillance
- Results in a persistent or significant disability/incapacity.
- Any other important medical event that may not result in death, be life threatening, or require hospitalization, may be considered a serious adverse experience when, based upon appropriate medical judgment, the event may jeopardize the subject and may require medical or surgical intervention to prevent one of the outcomes listed above. Examples of such medical events include allergic bronchospasm requiring intensive treatment in an emergency room or at home, blood dyscrasias or convulsions that do not result in inpatient hospitalization, or the development of drug dependency or drug abuse.

9.2.3 Procedures to be Followed in the Event of Abnormal Laboratory Test Values or Abnormal Clinical Findings

All positive tests for gonorrhea and chlamydia will be reported within 24 hours to the appropriate study personnel by the LACDPH laboratory. In the event of a positive test for gonorrhea, study personnel will contact the subject to arrange for treatment and discontinuation from the study. Test results will be reported by name to the LA County health department as required by law.

9.3 Reporting Procedures

All AEs specified in Section 9.2.1 including local and systemic reactions not meeting the criteria for “serious adverse events” will be captured on Adverse Event CRF. Information to be collected includes event description, time of onset, investigator assessment of severity, relationship to study product, and time of resolution/stabilization of the event. Adverse events must be documented appropriately regardless of relationship.

As noted in Section 9.2.1, medical conditions that are present at the time the subject is screened should be considered as baseline and not reported as an AE.

All Sexually Transmitted Infection Clinical Trials Group (STI CTG) protocols follow the NIAID guidelines for reporting of AEs. The FHI 360 Center for Data Management (CDM) will provide a listing of AEs to the Principal Investigator (PI) for review on a monthly basis. The CDM will

compile these events in a secure tabular format and forward them to the Protocol Specialist (PS) for posting on the study's SharePoint site within the STI CTG. The Protocol Team has access to the specific study SharePoint.

All serious adverse events will be immediately reported to the SI at each site and to the PI, [name]. In addition, SAEs should be reported to all pertinent IRBs according to their AE reporting guidelines. The CDM, the DMID Clinical Project Manager (CPM), and the PS should be notified within 24 hours.

All AEs that meet the expedited reporting requirements of NIAID are reported to DMID's pharmacovigilance contractor. These events will be referred to as SAEs. DMID's pharmacovigilance contractor will respond to SAEs and will disseminate reports to the DMID Medical Monitor, the PI, and the PS. It is the responsibility of each YCF to provide this information to the LA County IRB, if required.

9.3.1 Serious Adverse Events

All SAEs will be:

- recorded on the appropriate SAE form
- followed through resolution by a study physician
- reviewed by a study physician

SAEs must be documented from the first study intervention, Study Day 1 through the Day 28 follow-up visit.

Any AE that meets a protocol-defined serious criterion must be submitted within 24 hours of site awareness on an SAE form to the DMID Pharmacovigilance Group, at the following address:

Medical Affairs/Pharmacovigilance

DMID Pharmacovigilance Group
Clinical Research Operations and Management Support (CROMS)
[name] [name] 650
Bethesda, MD 20814, USA
SAE Hot Line: [name] (US)
SAE FAX [contact] (US)
SAE Email Address: [contact]

Questions about SAE reporting can be referred to the SAE Hotline (available 24 hours a day/7 days a week)

Other supporting documentation of the event may be requested by the DMID Pharmacovigilance Group and should be provided as soon as possible.

The DMID medical monitor and CPM will be notified of the SAE by the DMID Pharmacovigilance Group. The DMID medical monitor will review and assess the SAE for regulatory reporting and potential impact on study subject safety and protocol conduct.

At any time after completion of the study, if the investigator becomes aware of an SAE that is suspected to be related to study product, the investigator will report the event to the DMID Pharmacovigilance Group.

Plans for Assuring Compliance with Requirements Regarding the Reporting of Adverse Events (AE)

- The SC will transmit copies of all SAEs (including deaths) within the timeframes specified above. These events will be entered into an SAE database on a protocol-specific basis.
- Tabulations of SAEs will be electronically transmitted quarterly to NIAID/DMID with hard copies to the PI and to the NIAID Project Officer and to the NIAID Medical Monitor. These tabulations will consist of cumulative summaries of SAEs by type of event, severity grade, and relationship to study drug therapy.
- Sign-off by the NIAID Medical Monitor, PI, and NIAID Project Officer within 5 working days of receipt and returned to complete tracking process.

Plans for Assuring that any Action Resulting in a Temporary or Permanent Suspension of an NIAID-funded Clinical Trial is Reported to the NIAID Program Director Responsible for the Contract

In the event that termination of the trial or major modification to the protocol is under consideration, the PI will convene the protocol team and SI by conference call to discuss the options. The STI CTG Coordinating Center will inform the NIAID Program Director when studies are temporarily or permanently closed. All amendments to protocols must be approved by the NIAID.

9.3.2 Regulatory Reporting for Studies Not Conducted Under DMID-Sponsored IND

As this study will not be conducted under an Investigational New Drug Application (IND), MedWatch will be used to report related AEs. DMID will be copied simultaneously when an alternate method of reporting is utilized.

9.3.3 Other Adverse Events

Not applicable.

9.4 Type and Duration of Follow-up of Subjects after Adverse Events

AEs will be followed until resolution even if this extends beyond the study-reporting period. Resolution of an AE is defined as the return to pretreatment status or stabilization of the condition with the expectation that it will remain chronic.

9.5 Halting Rules

Findings that will alert the PI to conduct a safety review will include the number of SAEs overall, the number of occurrences of a particular type of SAE, and severe AEs/reactions. If the PI and the NIH Medical Monitor determine that the number of SAEs and severe AEs/reactions warrants investigation, the PI will immediately request that enrollment be halted until such an investigation has been completed. The study enrollment and dosing will be halted for Data and Safety Monitoring Board (DSMB) review if two study subjects develop the same study product related SAE.

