7.3 Follow-up Visit (Visit 2)

Prior to this visit, the study site personnel will review results of the AC2 from the enrollment visit and confirm the test was positive for *C. trachomatis*. Those participants with AC2 negative for *C. trachomatis* at the enrollment visit are removed from the study and will not participate in the follow-up visit. Participants who remain eligible will be asked to provide a first-catch urine specimen (approximately 20-30 ml) for chlamydia testing by AC2 at 28 days following initiation of the study drug regimen. Two aliquots of the urine sample will be stored at 0-10° C until shipped to UAB for OmpA genotyping and measurement of organism load. All specimens will be shipped to UAB. Aliquots from urine samples that test positive for *C. trachomatis* will undergo OmpA genotyping and organism load measurement. Aliquots from urine specimens that test negative for *C. trachomatis* will be discarded upon receipt at UAB.

Participants will be queried regarding any possible side effects of the study medication. Participants undergo a brief assessment on clinical parameters since enrollment. Per Section 3.1, the primary objective of the study is assessment of treatment outcome at the Day 28 follow-up visit (Visit 2). The study will enroll up to 446 males until complete data are obtained on at least 357 evaluable participants who are assessed at the Day 28 follow-up visit (Visit 2). Participants will be evaluated for the treatment outcome at Visit 2 according to the following definitions:

Microbiological Cure (treatment success):

AC2 is negative for *C. trachomatis* at the Day 28 follow-up visit (Visit 2).

Microbiological Failure (treatment failure):

- AC2 is positive for *C. trachomatis* at the Day 28 follow-up visit (Visit 2) and *C. trachomatis* OmpA genotyping reveals the baseline chlamydial strain and the repeat positive chlamydial strain to have the same *ompA* sequence (i.e., concordant).
- If a participant has discordant *ompA* sequences and no evidence for mixed strain infection, they will be classified as a new infection and not considered a microbiological failure.
- OmpA genotyping is not successfully performed on the baseline or repeat positive chlamydial isolate (i.e., there is an insufficient number of *ompA* copies in the sample to successfully amplify), but the participant did not have an unsupervised furlough (i.e., a

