8 STUDY PROCEDURES/EVALUATIONS

8.1 Clinical Evaluations

- Prior to enrollment, results and date of the screening chlamydia and gonorrhea test (part of juvenile intake procedure) will be obtained by study site personnel. Only those with a positive chlamydia test and negative gonorrhea test will be approached for possible enrollment.
- After consent is obtained, additional eligibility criteria will be determined. This includes assessing if participant has received antimicrobial therapy with activity against *C. trachomatis* within 21 days of positive chlamydia screening NAAT (or in the interval between the positive screening NAAT and study enrollment) and whether participant has epididymitis symptoms based on medical records. If a participant is noted to have received antimicrobial therapy with activity against *C. trachomatis* usage within 21 days of screening or has had a clinical diagnosis of epididymitis between screening and enrollment, then the participant is ineligible.
- Eligible participants will be enrolled and demographic information (race, ethnicity and date of birth), STD history, and sexual history will be recorded onto a data collection form at the enrollment visit.
- At the end of the enrollment visit, azithromycin 1 gm is administered to each participant and ingestion is directly observed and time of administration recorded.
- At the enrollment visit, counseling will be given regarding the importance of sexual abstinence during the course of the study.
- Prior to the follow-up visit, AC2 test results from the enrollment visit are reviewed to ensure continued eligibility.
- At follow-up visit, medical history including epididymitis symptoms, sexual history including sexual activity, information on furloughs, defined AEs (see Section 9.2.1), and SAEs are recorded. Results of AC2 testing at each visit are reviewed when they become available and are used for classification of treatment outcomes for that visit.

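### The discretionary halt in Section 9.5 counts severe AEs of any kind, but a severe, non-serious, non-gastrointestinal AE that does not end participation has no required AE CRF record

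*Combined protocol and SAP*

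**What the plan says.** **The halting rule.** Section 9.5 names three findings that alert the PI to conduct a safety review: the overall number of SAEs, "the number of occurrences of a particular type of SAE, and severe AEs/reactions". If the PI and the NIH Medical Monitor judge that the number of SAEs and severe events calls for investigation, the PI must at once ask for enrollment to stop. Separately, two participants with the same product-related SAE stop enrollment and dosing for DSMB review.

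**What is recorded.** Section 9.1 states that "we will not evaluate all AEs as an objective of the current study" and limits collection to GI symptoms and SAEs. Section 9.2.1 sends two classes to the AE CRF: GI AEs, and AEs that lead to discontinuation. SAEs go on their own form (9.3.1). Section 8.1 says that at the follow-up visit "defined AEs (see Section 9.2.1), and SAEs are recorded". Section 9.3 ties AE CRF capture to the events specified in 9.2.1, and 9.3.3 (Other Adverse Events) is marked not applicable.

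**What is asked at Visit 2.** Section 9.2.1 says that "subjects will be queried regarding the occurrence of any gastrointestinal side effects since enrollment visit". Section 7.3 words the query more broadly: "Participants will be queried regarding any possible side effects of the study medication".

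**How severity is graded.** Section 9.2.1 says "All AEs, as specified in Section 9.2.1, must be graded for severity and relationship to study product". GI events use Appendix B. For the rest, "Other AEs will be graded using the following general criteria", which are mild, moderate and severe.

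**The concern.** A halting rule should be fed by the events it counts. Section 9.5 lists severe AEs apart from SAEs and does not confine them to GI events, while the recording rules are confined to GI events, discontinuations and SAEs. Staff who follow the plan exactly could leave a severe, non-serious, non-GI event off the AE CRF. The number that the PI and the medical monitor are asked to judge could then be incomplete.

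The trigger for severe AEs has no numerical threshold. It rests on judgement, and so on which events those two people see. The participants are incarcerated and as young as 12, with a waiver of parental consent requested for minors (14.3.1), which is a further reason for the safety inputs to match the safety rule. Only safety recording is at stake; the efficacy comparison does not depend on it.

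**Working it through.** No arithmetic applies. The check sets the event classes that 9.5 counts against the records that the plan requires.

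| Event after dosing | Counted in 9.5? | Required record |
|---|---|---|
| SAE, any organ system | Yes | SAE form (9.3.1) |
| Severe GI AE, not serious | Yes | AE CRF (9.2.1) |
| Severe non-GI AE, not serious, causes discontinuation | Yes | AE CRF (9.2.1) |
| Severe non-GI AE, not serious, participation continues | Yes, as 9.5 is worded | None stated |

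**Can the last row occur?** Three definitions matter.

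1. Severe, for non-GI events, means that usual daily activity is interrupted, possibly with a need for systemic medication (9.2.1). Such events are described as usually incapacitating, but the definition requires neither seriousness nor withdrawal.
2. Serious (9.2.2) requires death, threat to life, hospitalization, lasting disability, or a medically important event that may need intervention to prevent one of these. Many severe events would qualify, but the two definitions are not the same.
3. Withdrawal for an AE (5.3.1) turns on the participant's best interest or the investigator's judgement. The treatment is one observed dose (6.2), with a single repeat if it is vomited, so there is normally no further drug to stop and a severe event need not end participation.

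The last row is therefore not empty by definition.

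**Does other text close it?**

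- Section 9.3 mentions local and systemic reactions, but only within the AEs specified in 9.2.1.
- Section 9.2.1 defines AEs broadly, says that AEs must be documented whatever their relationship to the drug, and says that doubtful observations should be reported. It names no form for this class.
- The severity scale for other AEs already has a use, namely non-GI AEs that cause discontinuation, so its presence does not imply wider capture.
- Section 9.3.2 (MedWatch for related AEs), 9.6 (IRB notification of possibly attributable AEs), 11.3.1 (a DSMB summary of any adverse events), 11.5 (AE incidence and severity for all subjects) and Appendix A (AE assessment, medical history and concomitant medication review at Visit 2) are not limited to GI events. None requires an AE CRF entry for this class.

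**Would the existing Visit 2 question elicit it?** Only in part. The 9.2.1 query is GI-only. The 7.3 query concerns possible side effects of the study drug, so an event that the participant does not link to the drug may not be mentioned.

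**The case against.** The best defence is that the plan can be read consistently. The restricted AE set is deliberate and justified in 9.1 by the predecessor trial in the same population, where no one on azithromycin had an SAE or withdrew for an AE. Later sections refer back to that set, so the severe events in 9.5 may be meant as severe events within it. That reading is possible, but 9.5 does not state it. If it is what the sponsor means, 9.5 needs a phrase to say so.

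The defence is right on several further points, and they limit the concern:

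- Section 9.5 does not make the AE CRF its only source. A reader might infer that an event missing from the CRF is lost to the safety review. The documents do not support that: the PI can be alerted by any of the routes listed above. What they support is that the event is not assured of reaching the PI's monthly listing.
- The foreseeable non-GI hazard, severe hypersensitivity (2.3.1), would often be an SAE; 9.2.2 gives allergic bronchospasm needing intensive treatment as an example.
- The severe-AE trigger is discretionary, so no fixed decision rule changes. The one automatic halt uses SAEs, which are captured.

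A reader might also try to size the gap from the predecessor, which reported no severe AEs (2.1). An upper bound from zero events would cover severe AEs of every organ system, including GI events that this trial does record. It would also depend on an assumption about who was assessed. It does not measure the unrecorded class.

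**Conclusion.** The mismatch is real but narrow. As written, a severe, non-serious, non-GI AE that does not end participation falls within 9.5 but has no required AE CRF record. The conclusion rests on taking 9.5 at its word, with no organ-system limit, and on the absence of any sentence elsewhere that requires the entry. The CRF itself is not among the documents, so whether it would in practice invite such an entry cannot be checked.

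No numerical size can be given. Few or no events are likely. This does not show that the halting provision fails or that the trial is unsafe, and the automatic two-SAE halt and the efficacy result stand. It is a cheap improvement in safety recording that is worth making.

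**What to change.** In 9.2.1, add a third class to those recorded on the AE CRF: any AE of severe grade from dosing through Visit 2, regardless of organ system or discontinuation. Sections 8.1 and 9.3 then follow, because both refer to 9.2.1. Adjust the statement of scope in 9.1 to match. Widen the Visit 2 query in 9.2.1 so that it elicits severe events of any type. Aligning it with 7.3 alone would not be enough, since 7.3 asks only about possible effects of the drug.

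If the sponsor instead means 9.5 to cover only SAEs, GI AEs and AEs causing discontinuation, say so in 9.5.

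The cost is a short amendment, a slightly broader Visit 2 question and a few more AE records. No extra visit is needed, the severity scale already exists, and the deliberate exclusion of minor non-GI AEs is kept. Whether the CRF needs a change would have to be confirmed by the data center.
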